9.5 Pregnancy Reporting

In the event of a pregnancy, the physician will notify the AbbVie MR within 24 hours of the physician becoming aware of the pregnancy.

AbbVie MR will send the AbbVie Pharmacovigilance department identified in Section 9.4.

10.0 Product Complaint

A Complaint is any written, electronic, or oral communication that alleges deficiencies related to the physical characteristics, identity, quality, purity, potency, durability, reliability, safety, effectiveness, or performance of a product/device after it is released for distribution.

The investigational product in this trial contains both:

- Biologic compound(s) and
- Device component(s) (pre-filled syringe, pen).

Complaints associated with any component of this investigational product must be reported to the Sponsor (Section 10.2.) For product complaints, please refer to Section 10.2.

10.1 Definition

A Product Complaint is any Complaint related to the biologic or drug component of the product or to the medical device component(s).

For a product this may include, but is not limited to, damaged/broken product or packaging, product appearance whose color/markings do not match the labeling, labeling

discrepancies/inadequacies in the labeling/instructions (example: printing illegible), missing components/product, device not working properly, or packaging issues.

For medical devices, a product complaint also includes all deaths of a patient using the device, any illness, injury, or adverse event in the proximity of the device, an adverse event that could be a result of using the device, any event needing medical or surgical intervention including hospitalization while using the device and use errors.

Any information available to help in the determination of causality by the device to the events outlined directly above should be captured.

10.2 Reporting

Product Complaints concerning the investigational product and/or device must be reported to the Sponsor within 24 hours of the study site's knowledge of the event via local Product Complaint reporting practices. Product Complaints occurring during the study will be followed-up to a satisfactory conclusion. All follow-up information is to be reported to the Sponsor (or an authorized representative) and documented in source as required by the Sponsor. Product Complaints associated with adverse events will be reported in the study summary. All other complaints will be monitored on an ongoing basis.

Product complaints involving a non-Sponsor investigational product and/or device should be reported to the identified contact or manufacturer, as necessary per local regulations. Product Complaints may require return of the product with the alleged complaint condition (syringe, pen, etc.). In instances where a return is requested, every effort should be made by the investigator to return the product within 30 days. If returns cannot be accommodated within 30 days, the site will need to provide justification and an estimated date of return.

The description of the complaint is important for AbbVie in order to enable AbbVie to investigate and determine if any corrective actions are required.

11.0 Ethics and Quality

In accordance to the code of conduct of MHLW/PMDA, the AbbVie GK will forward the PMOS protocol to the PMDA for approval. The PMOS result will also be reported to the PMDA.

All patient data entered in the patient's CRF will be forwarded to AbbVie GK for evaluation - without naming the patient. Each CRF bears a pre-printed patient identification number, which replaces the patient's initials. Accordingly, the patient's identity will not be disclosed to AbbVie GK.

In-house monitoring of incoming CRF pages with respect to completeness and plausibility will be done by the CRO responsible for data management and statistics. Queries to the study centers will be handled by the sponsor.

This PMOS will be sponsored by AbbVie GK. ([name])

12.0 Case Report Forms

All data specified in Section 8.5 "Study Conduct" will be collected on paper forms (CRF). For each visit, the CRF includes forms to be completed by the physician as well as forms to be completed by the patient. Each center receives a folder with all documents and forms necessary for the baseline and follow-up documentation of contract number of cases.

Any observation of an adverse event in the time period up to 104 weeks (or discontinuation of this study), beginning with the initiation of adalimumab therapy, is to be documented on the CRF. If the event fulfills the serious criterion (Serious Adverse Event), the "Serious Adverse Event Report" form is to be completed additionally.

13.0 Data Analysis Plan

All statistical analysis procedures will be described in detail in a Statistical Analysis Plan (SAP). This plan will be developed by the responsible biometrician in collaboration with the sponsor. The SAP will be finalized and approved by the responsible biometrician, the sponsor, and the principle investigator before the database will be opened for the first interim analysis.

13.1 Sample Size Calculation

The primary endpoint of this study is the proportion of subjects who achieve DAS28 (CRP) remission (DAS28 <2.6) after 52 weeks of adalimumab + high dose MTX. We calculated the target sample number for this survey on the basis of an expected remission

rate, i.e., the percentage of patients with a DAS28 score of <2.6, at week 52 during the treatment with adalimumab 40 mg and MTX at ≥ 12 mg/week.

Table 3 lists the percentages of patients with a DAS28 score of <2.6 at week 52 in a study conducted by Takeuchi et al.⁹⁾ in patients receiving adalimumab and MTX.

Table 3. Patients with a DAS 28 score of <2.6 at week 52 during the treatment with adalimumab and MTX

adalimumab + MTX dose (mg/week)	Percentage of patients with DAS28 <2.6 (Week 52)
8.5 ± 2.9	42.7% (61/143 patients)
≥ 12	61.7% (29/47 patients)

As Table 3 shows, 42.7% of patients receiving MTX at 8.5 ± 2.9 mg/week at the initiation of adalimumab treatment achieved a DAS 28 of <2.6 at week 52, and the corresponding percentage of patients receiving DAS at ≥ 12 mg/week at baseline was 61.7%. When 55% of patients receiving MTX at ≥ 12 mg/week at the initiation of adalimumab treatment are assumed to achieve a DAS 28 of <2.6 at week 52 (subtracting the standard error (7.10%) from the above mentioned percentage; $61.7 - 7.1 = 54.6\%$), the number of patients required to achieve a power ($1-\beta$) of 0.90 at an α level of 0.05 (two-tailed) would be 171 (one-sample test).

Since 32% of patients enrolled in the all-case survey of adalimumab in patients with rheumatoid arthritis dropped out during the 24-week survey period, we assumed that 50% of the participants in the survey would drop out during the 52-week survey period, and calculated that 342 patients should enroll in the survey. We thus set the target sample size at 350.

13.2 Analysis Population(s)

The data of all documented patients will be used in the statistical analysis of tolerability and safety.

13.3 Missing Values

Missing observations will be documented as missing values. Instructions for the minimum documentation required for a patient to be evaluable will be established in the

SAP.

All data will be analyzed on the basis of “observed cases”. For the statistical analysis of data concerning the course of disease (if related to changes from baseline values), an additional approach will be followed considering only patients with complete data at all visits.

13.4 Level of Significance

Inferential statistics will be performed at a nominal level of significance of 0.05 (two-sided).

13.5 Times of Statistical Analyses

Interim analyses are planned after 24 and 36 month after the inclusion of the first patients. The general analysis will be performed after closure of the follow-up of the last patient (4 years after starting the study).

14.0 Final Report and Publications

After the end of the study, an Integrated Final Report is generated in cooperation with the Principal Investigator. The report includes a description of the objectives of the study, the employed methods, the results, as well as the conclusions. As the property of AbbVie GK, the completed CRFs and the report are to be treated as confidential and may not be made accessible to unauthorized persons in any form (publication or presentation) without the explicit approval of AbbVie GK. The results of this study may be published by AbbVie GK or any of the participating investigators after approval by AbbVie GK.

2.00	2/15/2016		Changes in overall description methods Review of figures/tables and definitions in association in response to periodic safety report
3.00	3/15/2016		Review of figures/tables and definitions in response to reexamination
4.00	7/22/2016		Addition of figures/tables and definitions in response to periodic safety report
5.00	9/15/2017		Addition of figures/tables and definitions for the final analysis
6.00	4/9/2018		Addition of tables as adjustments prior to the implementation of the final analysis

2. Definition of terms and abbreviations

The terms and abbreviations used in this statistical analysis plan are defined as follows.

Terms and abbreviations	Definitions
Adverse event	An adverse event (AE) refers to any unfavorable and unintended sign (including an abnormal laboratory finding), symptom or disease occurred in patients, whether or not considered related to the drug used.
Adverse reaction	Adverse events for which a causal relationship with Humira cannot be ruled out were handled as adverse reactions (ADRs).
Summary statistics	Summary statistics include the number of patients, mean, standard deviation, minimum, median, maximum.
MedDRA/J	Medical Dictionary for Regulatory Activities / Japanese edition
SOC	MedDRA/J System Organ Class
PT	MedDRA/J Preferred Term
LLT	MedDRA/J Lower Level Term
ACR	American College of Rheumatology
CDAI	Clinical Disease Activity Index

Terms and abbreviations	Definitions
CRP	C-Reactive Protein
DMARDs	Disease Modifying Antirheumatic Drugs
DAS	Disease Activity Score
EQ-5D	EuroQol Questionnaire 5 Dimensions
EULAR	European League Against Rheumatism
ESR	Erythrocyte Sedimentation Rate
HAQ	Health Assessment Questionnaire
TSS	Total Sharp Score
mTSS	modified Total Sharp Score
MTX	Methotrexate
RA	Rheumatoid Arthritis
SDAI	Simplified Disease Activity Index
VAS	Visual Analog Scale
Children	Patients aged < 15 years
Adults	Patients aged between ≥ 15 years and < 65 years
Elderly	Patients aged ≥ 65 years

3. Purpose and rules of this statistical analysis plan

3.1. Purpose of preparation of this statistical analysis plan

The purpose of this statistical analysis plan is to predetermine the matters related to statistical analysis operation conducted in accordance with the protocol of the “Special Drug Use-Results Survey on Humira® For Subcutaneous Use 40 mg syringe 0.8 mL - Assessment of clinical effectiveness and safety of adalimumab and high dose methotrexate in routine clinical practice -” (hereafter, referred to as “this survey”). This is one of the surveys conducted in compliance with the GPSP Ordinance, and partial or total results of the analysis will serve as data used for reporting of the special drug use-results survey on Humira to authorities and preparation of application materials for reexamination.

4. Survey summary

4.1. Purpose of the survey

This survey is conducted in order to understand safety and efficacy in concomitant therapy with high dose ($\geq 12\text{mg/week}$) methotrexate (hereafter, referred to as “MTX”) in Japanese patients with rheumatoid arthritis (hereafter, referred to as “RA”) under the actual clinical conditions as a special drug use-results survey on Humira[®] For Subcutaneous Use 40 mg syringe 0.8 mL (nonproprietary name: Adalimumab) (hereafter, referred to as “Humira”).

4.2. Survey plan

(1) Survey subjects

Japanese RA patients who receive Humira meeting the following conditions.

- 1) Patients with the duration of RA within 2 years from the diagnosis at the start of Humira treatment
- 2) Patients receiving MTX for 3 months or longer at the start of Humira treatment
- 3) Patients receiving more than 12 mg/week of MTX at the start of Humira treatment
- 4) Patients with DAS28 (CRP) > 3.2 at the start of Humira treatment (4 weeks prior to treatment start - start date of treatment)

(2) Patients excluded from the survey

- 1) Patients who have received biological products

4.3. Planned sample size

(1) Planned number of patients surveyed

350 patients

(2) Rationale for setting

The patient with Disease Activity Score 28 (hereafter, referred to as “DAS28”) below 2.6 at week 52 was estimated to be 55% (the expected observation was 55% and the estimated difference was 12.3% for the literature data 42.7%), and the number of patients required to detect at a 5% level of significance level (paired) and a 90% power was calculated to be 171 patients. As the number needed to treat to secure this number of patients, the dropout rate at week 52 in this survey was assumed to be 50% based on the dropout rate of approximately 32% at week 24 in the all-case surveillance with Humira, and the planned number of patients surveyed was calculated to be 350 patients.

5. Items to be evaluated in analysis and examining method

(1) Analysis items

1) Matters concerning patient composition

- 1) Number of patients with returned CRFs
- 2) Number of patients included in the safety analysis set
- 3) Number of patients included in the efficacy analysis set

- 2) Matters concerning safety
 - 1) List of incidences of ADRs/infections
 - 2) Factors considered to have an influence on safety
Incidence of ADRs by patient background factor, etc.
 - 3) AEs occurred during or after treatment
List of incidences of serious AEs, etc.
 - 3) Matters concerning efficacy
 - 1) DAS28 response, trend, percentage of remission, etc.
 - 2) CDAI response, trend, percentage of remission, etc.
 - 3) SDAI response, trend, percentage of remission, etc.
 - 4) Trends in HAQ, etc.
 - 5) Trends in EQ-5D, etc.
 - 6) Trends in mTSS/bone erosion score/joint space narrowing score and the percentage of patients without worsening of mTSS/bone erosion score/joint space narrowing score (change from the survey start < 0 and < 0.5), etc.
 - 7) Factors considered to have an influence on efficacy (list of efficacy by patient background factor, etc.)
- (2) Analysis methods
Appropriate methods including χ^2 test according to the scale and nature of the analysis data should be used.

6. Schedule of the analysis

Purpose of the analysis	Survey unit period and time frame for reexamination
The 11th Periodic Safety Report	December 31, 2012 - June 30, 2013
The 12th Periodic Safety Report	July 1, 2013 - December 31, 2013
The 13th Periodic Safety Report	January 1, 2014 - June 30, 2014
The 14th Periodic Safety Report	July 1, 2014 - December 31, 2014
The 15th Periodic Safety Report	January 1, 2015 - December 31, 2015
The 16th Periodic Safety Report	January 1, 2016 - April 15, 2016
Application for reexamination	April 16, 2008 - April 15, 2016
Final Analysis	April 16, 2008 - July 31, 2018 (planned)

*Since there is no unit period for the final analysis, the proposed date for the final report is considered as the completion date.

7. Software/dictionaries used for analysis

7.1. Statistical analysis and tabulation software

The software and versions used for analyses are shown below.

	Software and versions
OS	Microsoft Windows 7 or a higher version should be used.
Statistical analysis software	SAS Ver. 9.2 or a higher version should be used.
Tabulation software	Microsoft Excel 2007 or a higher version should be used.

7.2. Dictionaries used

The dictionaries used for names of AEs and complications, and names of drugs are shown below.

Item	Names and versions of dictionaries	Remark
Types of AE and ADR/infection	Medical Dictionary for Regulatory Activities/Japanese edition (MedDRA/J) *An appropriate version should be used for aggregation according to the timing of analysis.	
 • AEs and ADRs/infections should be classified into System Organ Class (SOC), and appropriate terms should be selected from the Preferred Terms (PT) and described. • If indicating SOC, it should be indicated in accordance with the order of the international agreement.
Drug names (concomitant drugs)	Prescription drug name data file *An appropriate version is used for tabulation according to the time of analysis.	
 • When tabulating by concomitant drug name, nonproprietary names (seven-digit codes) should be used in principle; however, if there is no seven-digit code, therapeutic categories (the code with the highest digit among the available one-digit code, two-digit code, three-digit code or four-digit code) should be used where necessary.

8. Definitions of populations used for analysis

Name of population	Definitions
Patients enrolled	Patients who were confirmed to be enrolled.
Patients with returned CRFs	Patients whose CRFs are collected.
Patients with fixed CRFs	Patients whose CRFs are fixed.
Patients excluded from the safety analysis set	Patients meeting any of the conditions for excluding from safety analysis. Refer to the description in the “handling criteria of patients” of this survey for the conditions for exclusion from the safety analysis set.
Patients included in the safety analysis set	Patients with fixed CRFs except for the patients excluded from the safety analysis set
Patients excluded from the efficacy analysis set	Patients meeting any of the conditions for excluding from efficacy analysis. Refer to the description in the “handling criteria of patients” of this survey for the conditions for exclusion from the efficacy analysis set.
Patients included in the efficacy analysis set (DAS28-4CRP, DAS28-4ESR, CDAI, SDAI, HAQ-DI, EQ-5D.)	Patients included in the safety analysis set except for the patients excluded from the efficacy analysis set Among the patients included in the efficacy analysis set, the patients included in the efficacy analysis set according to each efficacy endpoint other than DAS28-4CRP indicated in the left should also be established.
Patients included in the efficacy analysis set (mTSS 52 weeks)	Among the patients included in the efficacy analysis set, patients whom mTSS was evaluated at week 52 reading session score.
Patients included in the efficacy analysis set (mTSS at week 104)	Among the patients included in the efficacy analysis set, patients whom mTSS was evaluated at week 104 reading session score.
Patients included in the efficacy analysis set (third CRF) (DAS28-4CRP, DAS28-4ESR, CDAI, SDAI, HAQ-DI, EQ-5D, mTSS)	
 (1) Patients included in the efficacy analysis set with the fixed third CRF. (2) Patients whom the final Humira treatment is later than week 52 + 4 weeks or later. (3) Patients with DAS28-4CRP measurement within the evaluation range from baseline and week 52 and after the lowest limit date within the evaluation range of week 76. 
Patients meeting three of the above conditions should be the patients included in the efficacy analysis set (third CRF).
 
In addition, among the patients included in the

Name of population	Definitions
	
efficacy analysis set (third CRF), patients with the measurements of the endpoints other than DAS28-4CRP and mTSS conducted at three time points: baseline, evaluation range of week 52, and after the latest limit date within the evaluation range of week 76 should be handled as the patients evaluated in the third CRF.
 
In mTSS, patients with the measurements of X ray score obtained at the second reading session conducted at three points: baseline, within the evaluation range of week 52, and after the latest limit date of the evaluation range of week 76 should be handled as patients evaluated in the third CRF among the patients included in the efficacy analysis set (third CRF) and patients included in the efficacy analysis set (mTSS at week 104).
 
Refer to “12. Handling of data on tests/evaluation time” for the range of evaluation time. The patients included in the efficacy analysis set by each efficacy endpoint other than DAS28-4CRP indicated in the left should also be established.

9. General agreements concerning analysis

9.1. Handling of missing data

Missing data should not be complemented in the analysis.

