7.3 Number of Patients to be Enrolled

The primary endpoint of this study is the proportion of subjects who achieve DAS28 (CRP) remission (DAS28 <2.6) after 52 weeks of adalimumab + high dose MTX. Based on data from another trial assessing the effectiveness of adalimumab in daily clinical practice, the following power calculation was done⁹⁾. With a significance level of 0.05 (two-sided) and a power of 0.90 (1-β), 350 subjects are required to detect an expected remission rate, i.e., the percentage of patients with the DAS28 score of <2.6 at week 52.

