7.5 Study Duration

- 1) The duration of the whole PMOS is estimated to be about 4 years.

- Study start: September 2012
-

- Recruiting phase: September 2012 - December 2014
 - Data completion: January 2018
 - End of study: The date on which statistical analysis dataset for Clinical Study Report becomes available
 - Data analysis and final report: April 2018 – October 2018
- 2) For each individual patient, the PMOS starts with the enrollment at the beginning of the treatment with adalimumab.
- Observation period
 - 104 weeks (or discontinuation of this study)
 - Discontinuation of this study
 - Patients within 52 weeks into this study: When adalimumab treatment is discontinued.
 - Patients after 52 weeks into this study: When any biologics other than adalimumab is administered.

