10.1. Overall

Name of data	Derivation and calculation methods
Age	The age on the start date of treatment should be calculated. However, if the birth date is unknown, the age described in the CRF should be used. Since it is obtained up to birth month and year in the CRF, the birth date should be the 1st of the month.
Number of survey institutions	It should be tabulated by institution code.
Number of patients surveyed	It should be tabulated by case (number).
Calculation of period	Period = the relevant date - the initial date +1
Definition of unit period	One week should be converted into seven days.
Date of initial Humira treatment	Of the start dates of treatment in Humira treatment status, the earliest date should be the date of initial Humira treatment.
Date of final Humira treatment	
Of the completion dates of treatment in Humira treatment status, the latest date should be the date of final Humira treatment.
 
However, the following measures should be taken according to the final record of each patient.
 
 • For patients whose the start date of treatment exceeds the planned completion date of each CRF and the completion date of treatment is described as “continuing,” the start date of treatment should be complemented to the complete date of treatment of the record. • For patients whose the start date of treatment is prior to the planned completion date of each CRF and the completion date of treatment is described as “continuing,” the completion date of treatment should be complemented to the complete date of treatment of each CRF. • If the start date of treatment with a biological product and the final record of the completion date of Humira treatment are the same date in the third CRF, the completion date of Humira treatment should be -1 day and the overlap of the treatment period should be deleted. 
*Planned completion date of each CRF First CRF: start date of Humira treatment + 167 days Second CRF: start date of Humira treatment + 363 days Third CRF: start date of Humira treatment + 727 days

Period to treatment completion (day)	It should be between the date of initial Humira treatment and the date of final Humira treatment.

Name of data	Derivation and calculation methods

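### The primary week-52 remission rate is planned only for patients with an on-treatment value; with 50% dropout assumed, no week-52 rate over the efficacy set stands beside it

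*SAP*

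**What the plan says.** **Endpoint.** Protocol sections 2.0 and 7.0 measure the primary objective by the percentage of patients with DAS28 below 2.6 at week 52. Sections 7.3 and 13.1 describe this as remission "after 52 weeks of adalimumab + high dose MTX".

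**Follow-up.** Protocol 7.5 defines when a patient leaves the study: "Patients within 52 weeks into this study: When adalimumab treatment is discontinued". Early stoppers are not followed to week 52.

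**Missing values.** Protocol 13.3: "All data will be analyzed on the basis of" observed cases. Its one additional approach, for changes from baseline, keeps only patients with complete data at every visit. SAP 9.1: "Missing data should not be complemented in the analysis".

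**Which values count.** SAP 12 takes week-52 data from day +336 to day +392, and only up to 28 days after the final adalimumab date (or to survey discontinuation, if earlier).

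**Expected loss.** Protocol 13.1: "we assumed that 50% of the participants in the survey would drop out during the 52-week survey period". SAP 4.3 agrees: "the dropout rate at week 52 in this survey was assumed to be 50" per cent.

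**Outputs.** SAP Table 6.2 gives the remission percentage with 95% CI by evaluation time in the DAS28-4CRP efficacy set. Table 1.2 (Appendix) counts evaluated and unevaluable patients per endpoint, Table 3.1 tabulates time to treatment completion, and Table 3.2.1 gives discontinuations and reasons in the first and second CRFs. For the literature analysis only, Tables 5.8.1 and 5.8.2 add retention curves and listing 8.1 gives final-evaluation scores per patient.

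**The concern.** The sample size allows for losing half the patients, but the primary output does not show what that loss does to the remission rate. A patient who stops adalimumab early leaves both numerator and denominator at week 52. A reader who takes the objective at its word, as a percentage of patients, would receive a percentage of those who stayed and were measured.

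Attrition itself is disclosed in the main analysis, with reasons. It is not linked to remission: no planned output gives the week-52 rate over the set, its confidence interval, or how far it moves with the way dropouts are counted. A reader could get the lower bound by dividing a count in one table by a set size in another. That gives no interval and does not separate recorded stoppers from patients who simply have no value.

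**Working it through.** **1. The plan's own figure.** Inputs from Protocol 13.1 and SAP 4.3: p0 = 0.427, p1 = 0.55, two-sided α = 0.05, power 0.90, one-sample test.

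n = [1.960·√(0.427·0.573) + 1.2816·√(0.55·0.45)]² / 0.123² = (0.9695 + 0.6376)² / 0.015129 = 170.7, so 171. With 50% dropout, 171/0.5 = 342, set to 350. Both figures reproduce. The 171 are patients observed at week 52, so the calculation agrees with an observed-case analysis.

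**2. Who can enter the week-52 rate.** The window opens at day 336, and data count to 28 days after the last treatment date. A patient whose last treatment date is before day 308 (336 − 28) cannot contribute.

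**3. Size of the gap.** Let d be the share without a week-52 value, p = 55% the observed remission rate, and q the unknown share in remission among the rest:

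rate over the set = (1 − d)·p + d·q.

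The size of the efficacy set is not given, because its exclusions are in a separate handling-criteria document. I use 350 as an upper limit. The 50% is the plan's week-52 assumption. The 32% is the week-24 dropout quoted from the all-case survey, used only as a lower case. Counts are rounded: 0.55 × 175 ≈ 96 and 0.55 × 238 ≈ 131. Intervals are Clopper-Pearson 95%.

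| | d = 50% | d = 32% |
|---|---|---|
| Observed cases | 96/175 = 54.9% (47.2–62.4) | 131/238 = 55.0% (48.5–61.5) |
| Over 350, all missing not in remission | 96/350 = 27.4% (22.8–32.4) | 131/350 = 37.4% (32.3–42.7) |
| Over 350, all missing in remission | (96+175)/350 = 271/350 = 77.4% | (131+112)/350 = 243/350 = 69.4% |

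If q equals p, the rate over the set is 55% at any d.

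**4. Smaller sets.** If the handling criteria remove patients with little follow-up, the gap narrows. With the same 96 of 175 observed:
- set of 250: 96/250 = 38.4% to (96+75)/250 = 68.4%
- set of 200: 96/200 = 48.0% to (96+25)/200 = 60.5%

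**5. The final-evaluation rate.** SAP 12 defines it as the last eligible value from day +1. For an early stopper that may be a score from the first months; for a patient who continues it is near week 104. Patients with no post-baseline value are left out. It covers most of the set, but not at week 52.

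**6. A trap in sorting the missing.** For a patient recorded as continuing whose start date precedes the CRF's planned end, SAP 10.1 says "the completion date of treatment should be complemented to the complete date of treatment of each CRF", and gives "First CRF: start date of Humira treatment + 167 days". A continuing patient with only a first CRF therefore gets a last treatment date of day +167. Adding 28 gives day 195, before day 336, so the derived date makes that patient look like an early stopper.

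**The case against.** **The plan is coherent.** The sample size is for observed patients, inflated for dropout and analysed as observed cases, in a single-arm observational study. This stands: the endpoint is not wrong, and the planned rate should stay primary.

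**A near-all-patient rate already exists.** A reader might infer that early stoppers appear in no remission rate at all. The documents do not support that. SAP 12 defines a final-evaluation time point, Table 6.2 reports by evaluation time, and Table 6.2.3, made in the manner of Table 6.1.3, carries a last-observation category. A last-observation remission rate therefore appears to be planned, although Table 6.2 does not list its evaluation times. It answers a different question, for the reason in step 5.

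**The direction is unknown.** A reader might infer that the observed-case rate overstates effectiveness. The recorded stop reasons in SAP 11 include inadequate response and adverse events, but also improvement up to complete remission, pregnancy and failure to attend. Counting every stopper as not in remission is one convention, and 27.4% and 77.4% are logical limits, not estimates.

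**The 42.7% reference.** It is tempting to note that 27.4% or 37.4% lies below it. That comparison is not made here: the documents do not say how the cited study counted its dropouts.

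**Unseen criteria.** The set size is unknown and Table 6.2 does not state its percentage denominator. The observed-case reading rests on Protocol 13.3 and SAP 9.1; it is the natural one, but an inference. This limits the size of the claim and supports asking for the denominator.

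**Conclusion.** The gap is real but limited. The primary week-52 rate is planned only as an observed-case rate in patients on adalimumab or within 28 days of the last treatment date, and no week-52 remission rate over the efficacy set accompanies it. At the plan's own 50% dropout, and with 350 as the upper limit for the set, a 54.9% observed rate is compatible with anything from 27.4% to 77.4% over the set; smaller sets or lower dropout narrow this. The result rests on the assumed 55% and 50%, on a set size that is not given, and on the observed-case reading of Table 6.2. It does not show that the planned rate is biased, or in which direction. This is a cheap improvement in reporting, not the correction of an error.

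**What to change.** In SAP Table 6.2:

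1. Keep the planned week-52 rate. State its denominator and label it as observed cases, on adalimumab or within 28 days of the last treatment date.
2. Add a supplementary week-52 rate with 95% CI over all efficacy-set patients with a baseline DAS28-4CRP. Count patients with a week-52 value as observed, and those without one who have a recorded discontinuation before week 52 as not in remission. Identify the latter by the SAP 10.1 definitions of discontinued and continuing patients, not by the derived last treatment date.
3. Give the number with no recorded discontinuation and no week-52 value. Show the rate with them counted as not in remission, and with them excluded.
4. Add one sensitivity row that uses the discontinuers' last on-treatment DAS28-4CRP, and cross-refer to Table 3.2.1 for stop reasons.

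The cost is a few SAP sentences and a few extra rows, from data already collected. The downsides are a little more tabulation and a supplementary figure that may look less favourable than the planned one.
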